9 ADVERSE EVENTS

9.1 Adverse Event

An AE is defined as any untoward medical occurrence associated with the use of an IP in humans, whether or not considered IP-related. An AE can be any unfavorable and unintended sign (e.g., an abnormal laboratory finding), symptom, or disease temporally associated with the use of an IP, without any judgment about causality. An AE can arise from any use of the IP (e.g., off-label use, use in combination with another drug or medical device) and from any route of administration, formulation, or dose, including an overdose. An AE can arise from any delivery, implantation, or use of a medical device, including medical device failure, subject characteristics that may impact medical device performance (e.g., anatomical limitations), and therapeutic parameters (e.g., energy applied, sizing, dose release, and anatomic fit) associated with medical device use.

All AEs spontaneously reported by the subject and/or in response to an open question from study personnel or revealed by observation, physical examination or other diagnostic procedures will be recorded in the source document and on the appropriate pages of the CRF. Any clinically relevant deterioration in clinical finding is considered an AE and must be recorded. When possible, signs and symptoms indicating a common underlying pathology will be noted as one comprehensive event.

Documentation regarding the AE will include the nature, date of onset, end date, severity, relationship to IP, action(s) taken, seriousness, and outcome of any sign or symptom observed by the investigator or reported by the subject upon indirect questioning. Exacerbation of conditions related to the signs and symptoms of DED will not be reported as an AE.

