9.1.2 Relationship to Investigational Product

The relationship of each AE to the IP will be determined by the investigator using these explanations:

- ***Related:*** A reasonable possibility exists that the IP caused the AE. A related AE can be further defined as follows:
 - Occurs within a reasonable temporal sequence to administration of study drug
 - Cannot be explained by concurrent disease or other drugs or chemicals
 - Improves or disappears on stopping or reducing study drug (de-challenge)
 - Reappears on repeated exposure to study drug (re-challenge)
 - Is an unusual event that is known to be associated with the drug or this class of compound, and cannot be explained by other therapy or the participant's physical condition
 - Unlikely to be attributed to concurrent disease or other drugs or a clinically reasonable response on withdrawal (de-challenge)
- ***Not Related:*** A reasonable possibility does not exist that the IP caused the AE. A not related AE can be further defined as follows:
 - Occurs with a temporal relationship to administration of study drug which makes a causal relationship improbable
 - Other drugs, chemicals or underlying disease provide plausible explanations of causality
 - Is known to be associated with the participant's clinical condition, or with other medication taken by the participant

Suspected adverse reaction means any AE for which there is a reasonable possibility that the IP caused the AE. "Reasonable possibility" means there is evidence to suggest a causal relationship between the IP and the AE. Types of evidence that would suggest a causal relationship between the IP and the AE event include: a single occurrence of an event that is uncommon and known to be strongly associated with IP exposure (e.g., angioedema, hepatic injury, Stevens-Johnson Syndrome); one or more occurrences of an event that is not commonly associated with IP exposure, but is otherwise uncommon in the population exposed to the IP (e.g., tendon rupture); an

aggregate analysis of specific events observed in a clinical trial (such as known consequences of the underlying disease or condition under investigation or other events that commonly occur in the study population independent of drug therapy) that indicates those events occur more frequently in the IP-treatment group than in a concurrent or historical control group.

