9.2 Serious Adverse Events

An AE is considered serious if, in the view of either the investigator or Sponsor, it results in any of the following outcomes:

- Death;
- Is life-threatening;

Note: An AE is considered "life-threatening" if, in the view of either the investigator or sponsor, its occurrence places the subject at immediate risk of death. It does not include an AE that, had it occurred in a more severe form, might have caused death.

- Inpatient hospitalization or prolongation of existing hospitalization;

Note: The term "inpatient hospitalization" refers to any inpatient admission (even if less than 24 hours), unless the inpatient admission was pre-planned prior to the signing of the informed consent. For chronic or long-term inpatients, inpatient admission includes transfer within the hospital to an acute/intensive care inpatient unit. Inpatient hospitalization does not include: emergency room visits; outpatient/same-day/ambulatory procedures; observation/short stay units; rehabilitation facilities; hospice facilities; nursing homes; or clinical research/phase 1 units.

Note: The term "prolongation of existing hospitalization" refers to any extension of an inpatient hospitalization beyond the stay anticipated or

required for the reason for the initial admission as determined by the investigator or treating physician.

- A persistent or significant incapacity or substantial disruption of the ability to conduct normal life functions;

Note: A serious adverse event (SAE) specifically related to visual threat would be interpreted as any potential impairment or damage to the subject's eyes (e.g., hemorrhage, retinal detachment, central corneal ulcer or damage to the optic nerve).

- A congenital anomaly/birth defect.

Important medical events that may not result in death, be life-threatening, or require hospitalization may be considered serious when, based upon appropriate medical judgment, they may jeopardize the subject and may require medical or surgical intervention to prevent one of the outcomes listed in this definition.

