9.3 Procedures for Reporting Serious Adverse Events

All SAEs and their outcomes, regardless of causality or expectedness, must be reported to █ and the Sponsor as required by the IRB/Independent Ethics Committee(IEC), federal, state, or local regulations and governing health authorities and recorded on the appropriate CRF. Adverse events will be collected from the time of the signing of the ICF until the follow-up phone call (about 7 days after the final day of randomized study drug treatment).

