9.3.2 Reporting a Serious Adverse Event

To ensure subject safety, all SAEs, regardless of relationship to the IP, must be immediately reported. All information relevant to the SAE must be recorded on the appropriate CRFs. The investigator is obligated to pursue and obtain information requested by █ and/or the Sponsor in addition to that information reported on the CRF. All subjects experiencing a SAE must be followed up and the outcome reported.

In the event of a SAE, the investigator will notify █ and the Sponsor immediately using the contact information below; obtain and maintain all pertinent medical records, information, and medical judgments from colleagues who assisted in the treatment and follow-up of the subject; provide █ and the Sponsor a complete case history, which includes a statement as to whether the event was or was not suspected to be related to the use of the IP; and inform the IRB/IEC of the SAE within their guidelines for reporting SAEs.

Contact information for reporting SAEs:

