15.1 Adverse Events

An AE is defined as any untoward medical occurrence associated with the use of an IP in humans, whether or not considered IP-related. An AE can be any unfavorable and unintended sign (e.g., an abnormal laboratory finding), symptom, or disease temporally associated with the use of an IP, without any judgment about causality. An AE can arise from any use of the IP (e.g., off-label use, use in combination with another drug or medical device) and from any route of administration, formulation, or dose, including an overdose. An AE can arise from any delivery, implantation, or use of a medical device, including medical device failure, subject characteristics that may impact medical device performance (e.g., anatomical limitations), and therapeutic parameters (e.g., energy applied, sizing, dose release, and anatomic fit) associated with medical device use.

All AEs spontaneously reported by the subject and/or in response to an open question from study personnel or revealed by observation, physical examination, or other diagnostic procedures will be recorded in the source document and on the appropriate pages of the CRF. Any clinically relevant deterioration in clinical finding is considered an AE and must be recorded. When possible, signs and symptoms indicating a common underlying pathology will be noted as one comprehensive event.

Documentation regarding the AE will include the nature, date of onset, end date, severity, relationship to IP, action(s) taken, seriousness, and outcome of any sign or symptom observed by the investigator or reported by the subject upon indirect questioning. Exacerbation of conditions related to the signs and symptoms of dry eye disease will not be reported as an AE. All AEs will be coded using MedDRA 22.0.

Treatment-emergent adverse events (TEAE) are defined as any event that occurs or worsens on or after the first dose of study treatment. Adverse events recorded in the eCRF which began prior to treatment will not be included in the summary tables but will be included in the AE data listings.

Severity of an AE is defined as a qualitative assessment of the degree of intensity of an AE as determined by the Investigator or reported to him/her by the subject. The assessment of severity is made irrespective of relationship to study drug or seriousness of the event and should be evaluated according to the following scale:

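### Dry-eye exacerbation is excluded from AE reporting without qualification, so non-serious worsening that is suspected drug-related or stops study drug has no clear route into the AE tables

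*Protocol*

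**What the plan says.** Protocol 9.1 sets two rules in consecutive paragraphs. The first is general: "Any clinically relevant deterioration in clinical finding is considered an AE and must be recorded". The second concerns the disease under study: "Exacerbation of conditions related to the signs and symptoms of DED will not be reported as an AE". SAP 15.1 repeats the general rule word for word and gives the exclusion as "Exacerbation of conditions related to the signs and symptoms of dry eye disease will not be reported as an AE". Neither document qualifies the exclusion or ranks the two rules.

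The later safety categories are all built on the AE:

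- Protocol 9.2: "An AE is considered serious if, in the view of either the investigator or Sponsor, it results in any of the following outcomes".
- Protocol 9.1.2: "Suspected adverse reaction means any AE for which there is a reasonable possibility that the IP caused the AE".
- Protocol 10.4.6 and SAP 15.1 define the TEAE as an AE that starts or worsens once study treatment has begun, and tabulate TEAEs that led to discontinuation.

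Protocol 9.1 asks for relationship, seriousness and action taken as part of AE documentation. SAP 15.8 examines maximum dose tolerability through the by-arm safety summaries and plans no further analysis for it.

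**The concern.** Some worsening of dry eye is ordinary fluctuation, and keeping that out of the AE tables is a reasonable choice. The exclusion as written does not stop there. It makes no exception for worsening that is serious, that the investigator suspects the drug caused, or that made the subject stop the drug.

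The line between exacerbation and drug reaction is hard to draw here. The Protocol's Introduction names burning, stinging, instillation-site pain and conjunctival hyperemia as reactions to existing dry-eye drugs. Burning/stinging, pain and conjunctival redness are also efficacy variables in this trial. Two sites could see the same event and, each following the text, one could record an AE and the other none.

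At stake is the local tolerability picture from a first clinical study. If events of this kind are classified as exacerbation, ocular TEAE and TEAE-discontinuation rates are too low. If the drug causes them, the shortfall falls mainly on the active arms.

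**Working it through.** The question is one of wording, so the check sets the rules side by side and follows each kind of event through them. The plan gives no figure to reproduce.

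**Step 1: which rule governs?** There are two readings.

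- *The deterioration rule governs.* Clinically relevant dry-eye worsening is an AE, and the exclusion covers only what is not clinically relevant. The exclusion does not say so.
- *The exclusion is an exception to the deterioration rule.* This is the more natural reading, since the specific rule follows the general one. All dry-eye exacerbation is then outside AE reporting, whatever its cause or consequence.

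The AE, SAE, discontinuation and readable safety-analysis sections of both documents contain no sentence that chooses between them.

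**Step 2: follow each event under the second reading.**

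- *Ordinary fluctuation.* Not an AE. No objection.
- *Serious worsening.* Protocol 9.2 builds the SAE on the AE, so the literal chain breaks. Against that, the note in 9.2 says an SAE "specifically related to visual threat would be interpreted as any potential impairment or damage" to the eyes, 9.2 also admits important medical events, and 9.3.2 says "all SAEs, regardless of relationship to the IP, must be immediately reported". An investigator would very probably report. No text says that these provisions override 9.1.
- *Non-serious worsening suspected to be drug-related.* Not an AE, so neither a suspected adverse reaction nor a TEAE. No counter-text exists.
- *Non-serious worsening that leads to stopping study drug.* Not an AE, so not a TEAE causing discontinuation. No counter-text exists. If the subject also leaves the study, the reasons listed in SAP 9 have no category for disease worsening, so the reason falls under a general heading such as subject request or Other.

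Express exceptions found: 0 of 3 (serious, suspected related, drug-stopping).

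**Step 3: consistency with the causality rules.** Protocol 9.1.2 accepts, as evidence of causality, an aggregate comparison showing that consequences of the underlying disease occur more often on drug than on control. Dry-eye worsening is such a consequence here. An AE-based comparison of that kind cannot be made for events the AE rules leave out.

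**Step 4: size.** The planned arm size is 60 (Protocol 10.3). One subject whose only event goes unrecorded changes the arm's TEAE rate by 1/60 = 0.0167, or 1.7 percentage points. This is a maximum: if the subject has another recorded TEAE, the overall rate does not change. The documents give no basis for the number of such subjects.

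**The case against.** The strongest reply is that this is no contradiction: a general rule is followed by a deliberate carve-out for the disease under study, whose worsening is measured repeatedly as efficacy. The first half is fair, and a reader who infers that the two sentences cannot both stand goes too far. But that reading settles the matter against the related and drug-stopping cases, because it excludes them plainly.

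A reader might infer that serious worsening would escape reporting. The documents do not support that. The visual-threat note and the duty to report all SAEs cover most of it; only the written override is missing.

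A reader might also infer that a subject who stops drug for dry-eye worsening leaves no trace but low compliance. That is not so. Protocol 8.5 requires a dosing deviation below 80% compliance. SAP 9 has a deviation category for non-compliance with study drug and a listing with date and description. Protocol 8.2 requires the reason for any concurrent medication. These records have limits: a late stop may stay above 80%, and a deviation is not an event with an assessed relationship. How the SAP counts exposure days and completers is a separate matter, unaffected by whether the event is an AE.

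The efficacy scales help in part. OSDI covers the past week, the 4-Symptom Questionnaire asks how the eyes feel in general, and observed-data tables and listings show individual worsening. None records relatedness or action taken. Under Protocol 7.1.3, subjects use no drops before the examinations at Visits 2 to 5, so scores at the visit do not directly capture a reaction to a drop.

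Two further points stand. Reactions to instillation fit the general AE definition, and Protocol 9.1.2 treats explanation by concurrent disease as counting against relatedness, so an event is lost only if a site calls it exacerbation. And SAP 15.2 to 15.7 are redacted; they may capture tolerability in other ways, which cannot be checked.

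**Conclusion.** The point holds in a limited form. Both documents exclude dry-eye exacerbation from AE reporting without qualification and do not reconcile this with the adjacent recording rule. The real gap is non-serious worsening that is suspected to be drug-related or that leads to stopping study drug: on the more natural reading it is not an AE and does not reach the AE-based summaries. For serious worsening, what is missing is an express statement of precedence.

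The effect on reported rates is at most 1.7 percentage points per affected subject in an arm of 60, provided that subject has no other TEAE. A reader might infer a known or large bias in the tolerability results. The documents do not support that, because they give no rate for such events and no share that sites would leave unrecorded.

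The conclusion assumes that some sites would apply the exclusion as written, and that the redacted text contains no exception. The AE and SAE definition sections are readable and contain none. This is a cheap improvement to the wording.

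**What to change.** In Protocol 9.1 and SAP 15.1, join the two sentences and qualify the exclusion, for example:

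*Exacerbation of dry eye disease is not reported as an AE unless it is serious, is suspected to be related to study drug (reactions to instillation included), or is a reason for stopping study drug; in those cases it is recorded as an AE. Apart from this exclusion, deterioration of clinical relevance is recorded as an AE. The SAE rules in Protocol 9.2 and 9.3 prevail over the exclusion.*

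Suspected relationship serves only to lift the exclusion; the general AE definition remains free of causality. The change concerns what is recorded and touches no treatment or stopping rule.

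The cost is one wording change in two documents and a reminder to sites. No new procedure, data item or table is needed. The downside is some additional AE records in all arms, probably few since ordinary fluctuation stays excluded; the vehicle arm gives a basis for interpreting them.

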9.1.1 Severity

Severity of an AE is defined as a qualitative assessment of the degree of intensity of an AE as determined by the investigator or reported by the subject. The assessment of severity is made irrespective of relationship to the IP or seriousness of the event and will be evaluated according to the following scale:

- ***Mild:*** Event is noticeable to the subject, but is easily tolerated and does not interfere with the subject's daily activities.
- ***Moderate:*** Event is bothersome, possibly requiring additional therapy, and may interfere with the subject's daily activities.
- ***Severe:*** Event is intolerable, necessitates additional therapy or alteration of therapy, and interferes with the subject's daily activities.

9.1.2 Relationship to Investigational Product

The relationship of each AE to the IP will be determined by the investigator using these explanations:

- ***Related:*** A reasonable possibility exists that the IP caused the AE. A related AE can be further defined as follows:
 - Occurs within a reasonable temporal sequence to administration of study drug
 - Cannot be explained by concurrent disease or other drugs or chemicals
 - Improves or disappears on stopping or reducing study drug (de-challenge)
 - Reappears on repeated exposure to study drug (re-challenge)
 - Is an unusual event that is known to be associated with the drug or this class of compound, and cannot be explained by other therapy or the participant's physical condition
 - Unlikely to be attributed to concurrent disease or other drugs or a clinically reasonable response on withdrawal (de-challenge)
- ***Not Related:*** A reasonable possibility does not exist that the IP caused the AE. A not related AE can be further defined as follows:
 - Occurs with a temporal relationship to administration of study drug which makes a causal relationship improbable
 - Other drugs, chemicals or underlying disease provide plausible explanations of causality
 - Is known to be associated with the participant's clinical condition, or with other medication taken by the participant

Suspected adverse reaction means any AE for which there is a reasonable possibility that the IP caused the AE. "Reasonable possibility" means there is evidence to suggest a causal relationship between the IP and the AE. Types of evidence that would suggest a causal relationship between the IP and the AE event include: a single occurrence of an event that is uncommon and known to be strongly associated with IP exposure (e.g., angioedema, hepatic injury, Stevens-Johnson Syndrome); one or more occurrences of an event that is not commonly associated with IP exposure, but is otherwise uncommon in the population exposed to the IP (e.g., tendon rupture); an

aggregate analysis of specific events observed in a clinical trial (such as known consequences of the underlying disease or condition under investigation or other events that commonly occur in the study population independent of drug therapy) that indicates those events occur more frequently in the IP-treatment group than in a concurrent or historical control group.

The investigator will initially classify the relatedness of an AE, but the final classification is subject to the Medical Monitor's determination unless revised by the Sponsor, which has the ultimate responsibility for judging relatedness.

9.1.3 Expectedness

The expectedness of an AE should be determined based upon existing safety information about the IP using these explanations:

- ***Unexpected:*** An AE that is not listed in the Investigator's Brochure (IB) or is not listed at the specificity or severity that has been observed.
- ***Expected:*** An AE that is listed in the IB at the specificity and severity that has been observed.
- ***Not applicable:*** An AE unrelated to the IP.

AEs that are mentioned in the IB as occurring with a class of products or as anticipated from the pharmacological/mechanical (or other) properties of the product, but are not specifically mentioned as occurring with the particular product under investigation are to be considered unexpected.

The investigator will initially classify the expectedness of an AE, but the final classification is subject to the Medical Monitor's determination.

9.2 Serious Adverse Events

An AE is considered serious if, in the view of either the investigator or Sponsor, it results in any of the following outcomes:

- Death;
- Is life-threatening;

Note: An AE is considered "life-threatening" if, in the view of either the investigator or sponsor, its occurrence places the subject at immediate risk of death. It does not include an AE that, had it occurred in a more severe form, might have caused death.

- Inpatient hospitalization or prolongation of existing hospitalization;

Note: The term "inpatient hospitalization" refers to any inpatient admission (even if less than 24 hours), unless the inpatient admission was pre-planned prior to the signing of the informed consent. For chronic or long-term inpatients, inpatient admission includes transfer within the hospital to an acute/intensive care inpatient unit. Inpatient hospitalization does not include: emergency room visits; outpatient/same-day/ambulatory procedures; observation/short stay units; rehabilitation facilities; hospice facilities; nursing homes; or clinical research/phase 1 units.

Note: The term "prolongation of existing hospitalization" refers to any extension of an inpatient hospitalization beyond the stay anticipated or

required for the reason for the initial admission as determined by the investigator or treating physician.

- A persistent or significant incapacity or substantial disruption of the ability to conduct normal life functions;

Note: A serious adverse event (SAE) specifically related to visual threat would be interpreted as any potential impairment or damage to the subject's eyes (e.g., hemorrhage, retinal detachment, central corneal ulcer or damage to the optic nerve).

- A congenital anomaly/birth defect.

Important medical events that may not result in death, be life-threatening, or require hospitalization may be considered serious when, based upon appropriate medical judgment, they may jeopardize the subject and may require medical or surgical intervention to prevent one of the outcomes listed in this definition.

